### C8. Statistical Considerations:

Power analysis was completed for the primary outcome of percentage reduction in average cigarettes per day smoked in the last week of sampling, and based on data from [name] previous e-cigarette sampling trial during which participants received a low power (1st Gen) device with one of two nicotine concentrations (low or high). We hypothesize that the impact of nicotine concentration on CPD reduction would be similar here for the low power groups and that the effect would be reversed, but of similar size, in the high-power groups (Figure 3a). The hypothesized interaction is shown during the last week of sampling for simplicity in Figure 3b, specifically that for the low power setting, a higher concentration will produce a larger decrease in cigarettes per day than the low concentration, but for the high-power setting, a higher concentration will produce a smaller decrease in cigarettes per day than the low concentration. We use the methods described by Fleiss for estimating power for interaction effects. As he notes, the variance of an interaction effect is four times that of the corresponding main effect. Thus, even large effects require large sample sizes to yield adequate power. In this case, a sample size of 40 participants / group will provide 80% power to detect an interaction among the two factors with a 0.050 significance level, assuming that the common standard deviation is 38% reduction in CPD, as was the case in [name] trial. However, we inflate this sample size by 10%, accounting for attrition over time, and thus aim to **recruit 45 participants randomized per group (total N=180)**.

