## Statistical Analysis Plan

Power analysis was completed for the primary outcome of percentage reduction in average cigarettes per day smoked in the last week of sampling, and based on data from [name] previous e-cigarette sampling trial during which participants received a low power (1st Gen) device with one of two nicotine concentrations (low or high) (84). We hypothesize that the impact of nicotine concentration on CPD reduction would be similar here for the low power groups and that the effect would reversed, but of similar size, in the high-power groups. In this case, a sample size of 40 participants / group will provide 80% power to detect an interaction among the two factors with a 0.050 significance level, assuming that the common standard deviation is 38% reduction in CPD, as was the case in [name] trial (84). However, we inflate this sample size by 10%, accounting for attrition over time, and thus aim to **recruit 45 participants randomized per group (total N=180)**.

For aims 1 and 2, we will assess the impact of concentration and power on each outcome across time using a generalized estimating equation that includes concentration, power, sampling week (time), and their interactions. Hypothesis 1 will focus on percentage reduction in CPD, Hypothesis 2 will focus on e-cigarette uptake (puffs per day), and Hypothesis 3 will focus on complementary measures of preference/demand, all of which are captured at Visit 4. Outcomes that are skewed (e.g., demand parameters, urinary cotinine) will be log transformed. It is possible that reductions in CPD will be bimodal in the last week of sampling, reflecting a subset of participants who may quit smoking during the trial. In this case, we would conduct a Chi-square test on the proportion of participants who reduce their smoking by at least 50%. Exploratory analyses on age will be conducted by adding age to the model. As described in the Career Development Plan, [name] (co-mentor) will be meeting with [name] monthly for training in these analyses, and will also be available to assist with any unexpected issues. Gender will be examined separately as a direct or moderating influence on all outcomes.

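### Hypothesis 1 may move from the powered continuous interaction to an unpowered, undefined Chi-square on a 50% cut, depending on the observed shape of the primary outcome and with no stated rule

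*Combined protocol and SAP*

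**What the plan says.** The SAP sizes the trial on the "primary outcome of percentage reduction in average cigarettes per day smoked in the last week of sampling". It states that "a sample size of 40 participants / group will provide 80% power". The target of that calculation is the interaction of concentration and power, tested at the 0.050 level. The variability comes from an earlier sampling trial, "assuming that the common standard deviation is 38% reduction in CPD". The effect is given only as a pattern: an effect of concentration in the low-power groups, and in the high-power groups "that the effect would reversed, but of similar size, in the high-power groups". The analysis for both aims is a GEE with concentration, power, week and their interactions.

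The SAP then adds a conditional: "It is possible that reductions in CPD will be bimodal in the last week of sampling", because some participants may quit. "In this case, we would conduct a Chi-square test on the proportion of participants who reduce their smoking by at least 50" per cent. Section C8 carries the same conditional and the same power statement ("a sample size of 40 participants / group will provide 80% power to detect an interaction").

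Neither place defines bimodality or says who judges it, or whether the judgement is made on pooled data without sight of the groups. Neither says whether the Chi-square replaces or accompanies the GEE, which groups it compares, or on how many degrees of freedom. Section C5a blinds participants and research staff to assignment and does not mention the analyst.

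**The concern.** The stated power belongs to one test: the interaction contrast on the continuous outcome. The conditional lets the test of Hypothesis 1 become a different one, on a dichotomised outcome, after the primary outcome has been looked at. Three things are at stake.

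- **Power.** Nothing in the documents shows what power the fallback has. A 50% cut discards how far each participant reduced.
- **Target.** Hypothesis 1 is an interaction. A Chi-square on four proportions, taken literally, tests any difference among the groups.
- **Error rate.** With no rule for the choice, the plan does not rule out the choice being influenced by the results, so it does not by itself secure the 0.050 level.

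**Working it through.** **1. The plan's own figure.** The text gives no numerical effect and Figure 3 is not shown, so 40 per group at 80% cannot be reproduced independently. It can only be back-solved (two-sided 0.05 assumed):

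- SE of the difference of differences = 2 × 38 / √40 = 12.02.
- Detectable contrast = (1.960 + 0.842) × 12.02 = 33.7 points, or about 16.8 points at each power level.
- Attrition: 40 / 0.90 = 44.4, rounded up to 45; 4 × 45 = 180. This agrees with the plan.

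**2. Fallback power if the outcome were normal.** Assume an overall mean reduction of 33% (not in the documents). Cell means are 33 ± 8.4 = 24.6 and 41.4.

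- P(reduction ≥ 50%) = 25.2% and 41.1%.
- Contrast = 2 × (0.411 − 0.252) = 0.318.
- SE = √[2 × (0.252 × 0.748 + 0.411 × 0.589) / 40] = 0.147; z = 2.17; power = Φ(2.17 − 1.96) = 58%.
- For assumed means of 20-50% the range is 51-62%.

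A normal outcome is not what opens this branch, so step 3 matters more.

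**3. Fallback power if the outcome is bimodal.** Assume a fraction q quit (100% reduction) and the rest have mean m and SD s. Then:

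- cell mean = 100q + (1 − q)m
- variance = q(1 − q)(100 − m)² + (1 − q)s²
- P(≥ 50%) = q + (1 − q)Φ((m − 50)/s)

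Take s = 22 and average q = 0.30. Both rows below hold the mean contrast at 2 × 16.8 = 33.6 points.

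| Where the effect lies | q (two cell types) | m | Mean contrast | 50% cut, 1 df |
|---|---|---|---|---|
| Quitting only | 0.195 / 0.405 | 20 / 20 | SE 12.70, z 2.65, power 75% | 26.5% v 45.6%, z 2.58, power 73% |
| Half in quitting, half in partial reduction | 0.2475 / 0.3525 | 14 / 26 | SE 12.85, z 2.61, power 74% | 28.6% v 44.2%, z 2.08, power 55% |

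Simulation of the first row (40,000 trials) gave 74.7% and 72.4%. Simulations with other assumed mixtures at 40 per cell show the same pattern (mean contrast v 1-df binary test):

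- Effect only in quitting: 75-79% v 72-78% in one set; 82% v 82% and 72% v 69% in another.
- Effect shared with partial reducers: 84% v 70%.
- Effect only among partial reducers: 62% v 32%.

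**4. If the Chi-square is an ordinary four-group test (3 df).** Power is 35-43% with normal data and 55-60% with quitting-only mixtures. Across the wider set of bimodal mixtures it is about 19-65%. Spreading the same effect over 3 df would cut the continuous test itself from 80% to 64%, so part of this loss comes from testing the wrong hypothesis.

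**5. Type I error.**

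- Switching on the pooled shape alone: 4.8-5.3%.
- Reporting the smaller of the two p-values: for two z statistics with correlation ρ, the chance that either exceeds 1.96 in size is 8.1% at ρ = 0.75 and 7.0% at ρ = 0.90. Simulated values were 7.8-8.2% (normal) and 7.0-7.7% (bimodal) with the 1-df test, and 8.3-8.8% with the 3-df test.

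**6. Is the switch needed?** Under the null with bimodal data at 40 per cell, the comparison of means had 5.0-5.4% type I error. Bimodality does not invalidate it.

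**The case against.** The strongest reply is that the branch opens only when quitters form a second mode, and that in that setting the 50% cut costs almost nothing. This stands for an effect that works only through quitting: the difference there is a few points, and with tightly grouped partial reducers the binary test can be slightly better (84-88% v 82-86% in one set of runs). But a visible second mode does not mean that the whole effect sits in it. The half-and-half row keeps the planned contrast and still loses 19 points.

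A second reply is that the case with the effect only among partial reducers is not like for like, because the mean test itself has just 62% there. That is fair. It shows the direction of the loss more than its size at the planned effect.

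A third is that looking at pooled shape does not inflate error, and that the 50% cut is fixed in advance, so the cutpoint cannot be shopped for. Both are correct. What remains is that the plan does not promise a pooled or blinded look.

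Three stronger readings do not hold. A reader might infer that power falls to 58% on this branch; that figure needs a normal, unimodal outcome, an assumed mean near 33% and a 1-df contrast that the plan does not specify. A reader might infer that the plan runs at 8% error; that requires running both tests and reporting the better one, which the plan does not propose. And a reader might take it as settled that the Chi-square replaces the GEE; replacement is the natural reading, but the text does not say so. If it is an addition, Hypothesis 1 has two tests and no stated order between them.

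**Conclusion.** The point holds as a defect of specification with a scenario-dependent cost, and it should be corrected. The 80% power statement covers only the continuous interaction. On the fallback branch, a 1-df test on the 50% cut ranges from no material loss (effect entirely in quitting) to a loss of roughly 14-30 points (effect partly or wholly among partial reducers). A four-group test has about 19-65% power and does not answer Hypothesis 1. Type I error is near 5% under a pooled, blinded choice and about 7-9% in the worst case of selective reporting, which the plan leaves open. Against this the switch offers no material gain.

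These figures assume a two-sided 0.05 level, equal cells of 40, an effect back-solved from the stated 80%, and illustrative bimodal mixtures that are not in the documents. The GEE is represented by its last-week interaction contrast.

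**What to change.** Delete the conditional in C8 and in the SAP. State instead that the GEE concentration-by-power contrast on last-week percentage CPD reduction, with robust standard errors (which the SAP does not now mention), is the primary test whatever the shape of the distribution. Add that the proportion reducing by at least half is reported in every case as a supportive analysis, tested as a concentration-by-power interaction.

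The cost is two sentences in each place. The drawback is that a mean is a less vivid summary when many participants quit; the supportive analysis shows that pattern. If the conditional is kept, a bimodality criterion fixed in advance and applied to pooled, blinded data would deal with the error rate. It would still need a defined interaction test and its own power.
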